7.2.5 Side Effects

Most common adverse reactions (incidence > 10%) are nausea, constipation, dry mouth, somnolence, dizziness, and vomiting. Complete and updated information is available in the investigational drug brochure and/or product package insert.

https://www.accessdata.fda.gov/drugsatfda_docs/label/2010/022370s000lbl.pdf

7.2.6 Rationale for Using Oral Tramadol with Transdermal Buprenorphine

Tramadol is being used for breakthrough pain as TD buprenorphine is long acting.

7.2.7 Dose adjustments in renal failure

No dose adjustment of tramadol is required for creatinine clearance >30ml/min. Creatinine clearance <30ml/min: restrict maximum daily dose of tramadol immediate release to 200 mg/day.

7.2.8 Dose Adjustment in Liver Failure

No dose adjustment is required in mild to moderate liver failure (Child Pugh class A and B).

Restrict dose to 50 mg q12 in severe liver impairment. **Refer to Table 4**

Table 4. Dose Modifications of Buprenorphine and Tramadol

Table 4:	Buprenorphine Patch	Oral Tramadol
Organ Impairment		
Renal: Creatinine clearance >30ml/min.	No dose adjustment.	No dose adjustment.
Renal: Creatinine clearance <30ml/min.	No dose adjustment.	Restrict maximum daily dose of tramadol immediate release to 200 mg/day.
Mild to moderate liver failure (Child Pugh class A and B).	No dose adjustment.	No dose adjustment.
Severe liver failure (Child Pugh C).	Not studied in severe impairment.	Restrict dose to 50 mg q12 in severe liver impairment.
Cytopenia's (any grade).	No dose adjustment required.	No dose adjustment required.
Other side effects, such as severe nausea, vomiting, headache, respiratory depression, somnolence, dizziness, and constipation.	Dose adjustment at clinician's discretion.	Dose adjustment at clinician's discretion.
Prolonged QTc>500 msec attributable to buprenorphine (other causes ruled out).	Hold buprenorphine patch until QTc comes back to normal range <470 msec	Not applicable

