4.11 Discontinuation of Study Treatment, Withdrawal, and Compliance

Discontinuation from the study treatment does not mean discontinuation from the study. The subject will be considered in follow-up, study procedures should still be completed as indicated by the study protocol, and AEs/SAEs will continue to be reported according to this protocol.

In the absence of treatment delays due to adverse events, study treatment/intervention may continue until:

- General or specific changes in the subject's condition renders the subject unacceptable for further treatment in the investigator's judgment.
- An inter-current illness that prevents further treatment administration.
- The subject decides to withdraw from the study.
- The subject has significant noncompliance with the protocol (see below).
- Unacceptable adverse event(s) and/or dose level reduction beyond requirements as detailed in this protocol.
- The clinical need for concomitant therapy that is not permitted in the study.
- Subjects who sign the informed consent form, enroll, and receive the study intervention, but subsequently withdraw, or are withdrawn or discontinued from the study will not be replaced.

Consent Withdrawal

A subject may decide to withdraw from the study at any time. MCWCC CTO will follow their IRB of record's SOPs regarding consent withdrawal.

If a subject intends on withdrawing consent, staff should confirm which of the following options the subject chooses and document the discussion:

- Full consent withdrawal, with no study follow-up.
- Selective consent withdrawal from the interventional portion of the study but agree to continued follow-up of associated clinical outcome information.

Investigator-initiated Withdrawal

The investigator will withdraw a subject whenever continued participation is no longer in the subject's best interests. Reasons for withdrawing a subject include, but are not limited to, disease progression, the occurrence of an adverse event or a concurrent illness, a subject's request to end participation, a subject's noncompliance, or simply significant uncertainty on the part of the investigator that continued participation is prudent. The reason for study withdrawal and the date the subject was removed from the study must be documented.

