5.2 Dose Determination for Buprenorphine and Tramadol

Based on our clinical experience and earlier studies barring exceptions, the typical MEDD dose of standard-of-care regimens, such as oxycodone, morphine and fentanyl patch used in the treatment of radiation-induced mucositis can range from 20 to 90 mg. Buprenorphine is a potent opioid substitute but there is no consensus at equipotency ratio for morphine to transdermal buprenorphine. Some authors have reported that it lies somewhere between 75:1 to 100:1.(34) This makes finding the appropriate morphine equivalent daily dose (MEDD) for buprenorphine in controlling mucositis-related pain a challenging task. For our study, we used 75:1 equipotency ratio to calculate our morphine equivalent daily dose (**Table 1**). As transdermal buprenorphine is a long-acting medication, we plan to allow tramadol 50 mg (total daily dose) as needed for breakthrough pain up to 400 mg/day (total daily dose), which roughly translates to 5 mg to 40 mg MEDD. Steady-state plasma buprenorphine concentration levels are achieved by day 3, during the first application of buprenorphine. Therefore, it can be titrated after a minimum of 72 hours. We hope to evaluate the possibility of using tramadol to facilitate dose adjustment of buprenorphine. With the buprenorphine and tramadol combination, we hope to provide MEDD to patients which is comparable to other standard-of-care opioids. There is no clear consensus definition of adequate and inadequate pain relief in this setting. However, it is well known that a VAS pain score of $\leq 3/10$ is considered mild intensity pain in multiple settings. Based on some earlier studies and the titratability of TD buprenorphine dose, we have defined adequate analgesia as VAS $\leq 3/10$ for 72 hours, inadequate analgesia as VAS $> 3/10$ for 72 hours, and unbearable pain as VAS $> 3/10$ for 96 hours.(16, 17) If patients have unbearable pain (VAS $> 3/10$ x 96 hours) despite being on highest dose of the buprenorphine patch and tramadol, then, we will switch from tramadol to oxycodone for breakthrough pain and continue treatment with buprenorphine. We will titrate this combination as needed for pain control until study completion. Some authors have also shown the benefit and safety of using immediate-release oxycodone in conjunction with transdermal buprenorphine for moderate to severe pain.(35) If the pain is still uncontrolled $> 3/10$ for 72 hours, even after using oxycodone 90 mg/day with buprenorphine 20 μ g/hour, then, the patient will be taken off the study regimen. However, data monitoring will continue. Patients suffering intolerable side effects (severe constipation, vomiting, headache, pruritis, sedation, or respiratory depression, etc.) or those who wish to switch to standard-of-care oxycodone due to ineffective pain control or unclear reasons at any time during the study will be taken off study regimen. However, data monitoring through the pain app and questionnaires will continue. The dose titration schedule is illustrated in **Table 2**.

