6.2.2 Reporting of Adverse Events and Serious Adverse Events

Please refer to Table 3 below to identify adverse events that meet reporting requirements. All serious adverse events (SAEs) that occur after the subject has signed the consent form through 30 days post last dose of study drug(s) will be reported. All SAEs will be followed until satisfactory resolution, or until the investigator deems the event to be chronic. All serious adverse events (SAEs) must also be documented in OnCore®.

Table 3: Adverse Events and Serious Adverse Events Reporting Requirements.

Attribution	SAE				AE		
	Grade 1, 2 & 3		Grade 4 and 5		Grade 3	Grade 4	
	Expected	Unexpected	Expected	Unexpected	Unexpected	Expected	Unexpected
Unrelated Unlikely	IRB ¹ and DSMC- Routine Review ²	IRB ¹ and DSMC- Routine Review ²	IRB ¹ - Routine Review ²	IRB ¹ - Routine Review ² DSMC ³ - Within 5 calendar days	DSMC ² - Routine Review	DSMC ³ - Within 5 calendar days	DSMC ³ - Within 5 calendar days
Possible Probable Definite	IRB ¹ and DSMC ³ - Within 5 calendar days	IRB ¹ and DSMC ³ - Within 5 calendar days	DSMC ³ - Within 5 calendar days	IRB ¹ and DSMC ³ - Within 5 calendar days			

Footnotes

¹ Guidance on adverse event reporting to the IRB will follow the current [MCW IRB Policies and Procedures](#).

² For routine reporting, the events will be reported to IRB as part of the annual continuing progress report, and the DSMC will review events entered in OnCore™ at the time of scheduled monitoring.

³ For expedited DSMC reporting, study coordinator/research nurse must notify the DSMC via email. For AEs, include the subject ID, date of event, grade, relatedness, expectedness, and a short narrative. For SAEs, DSMC will review the SAE report entered into OnCore™.

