7.1.5 Side Effects

Common side effects (>5%) of buprenorphine include nausea, vomiting, constipation, drowsiness, dizziness, headache, and sweating. It may also cause central nervous system depression, respiratory depression, and QT prolongation. Anticholinergic side effects like dry mouth, miosis, orthostatic hypotension, and urinary retention are also seen. Transdermal patches are also associated with contact dermatitis in some individuals. (42) If QTc prolongation of more than 500 ms is noticed, then, buprenorphine should be held until it is less than 470 ms. If respiratory depression is observed, then, remove buprenorphine patch, give oxygen, administer IV naloxone 2 mg stat over 90 secs in the hospital or urgent care setting.

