7.1.6 Special Considerations

It is not recommended in pregnant and lactating women, as it is category C medication, and it does pass into breast milk.

HIV:

Since many HAART drugs also affect the liver microsomal enzymes, healthcare workers should closely monitor liver function and drug levels in patients who have buprenorphine prescribed at the same time. In some patients, the dose of buprenorphine may require alteration.

Hepatitis:

Both hepatitis B and C are common comorbid conditions in opioid-dependent patients. Since buprenorphine break down occurs in the liver, these patients should have their liver function and drug levels closely monitored. Clinicians should caution patients with hepatitis that intravenous use of buprenorphine has correlations with liver damage.

Complete and updated information is available in the investigational drug brochure and/or product package insert.

Others: Specific patient populations, such as the elderly, debilitated patients, or those with pre-existing pulmonary disease are at greater risk of respiratory depression with buprenorphine. It should be used with extreme caution in these individuals.

7.1.7 Dose Adjustments: No dose adjustments for liver or renal impairment required for TD buprenorphine. Refer to **Table 3**.

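### Table 4 leaves respiratory depression to the clinician's discretion, which is looser than the patch removal and rescue required by section 7.1.5 and the withdrawal from the regimen in section 5.2

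*Combined protocol and SAP*

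**What the plan says.** Three places in the protocol say what to do when respiratory depression occurs on the regimen.

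- **Section 7.1.5 (buprenorphine side effects):** "If respiratory depression is observed, then, remove buprenorphine patch, give oxygen, administer IV naloxone 2 mg stat over 90 secs". The naloxone is to be given in a hospital or urgent-care setting. The trigger is observation alone; no grade is attached, and tramadol is not mentioned.
- **Section 7.2.8, Table 4 (dose modifications for both drugs):** the event sits in the row "Other side effects, such as severe nausea, vomiting, headache, respiratory depression, somnolence, dizziness, and constipation". The entry in both drug columns leaves dose adjustment to the clinician. Removing or holding the patch is not mentioned.
- **Section 5.2:** "Patients suffering intolerable side effects (severe constipation, vomiting, headache, pruritis, sedation, or respiratory depression, etc" and so on are to be taken off the study regimen, while pain-app and questionnaire data continue to be collected.

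Section 4.11 lists a general ground for ending study treatment: "Unacceptable adverse event(s) and/or dose level reduction beyond requirements as detailed in this protocol". It does not name respiratory depression.

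**The concern.** Table 4 is where a treating clinician would look for what to do with the dose after a toxicity. For this event it is more permissive than the drug's own side-effect section. Someone relying on the table could keep the patch in place or step down to a lower strength when 7.1.5 calls for removal and rescue.

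The difference matters clinically because of how the patch behaves. Section 7.1.2 says it releases drug continuously over seven days. After removal, concentrations take about 12 hours to halve and then decline with an apparent half-life of about 26 hours. A lower-strength patch goes on delivering drug, so it is not equivalent to removal. Section 5.1 adds that all study treatment is given to outpatients and that doses are titrated by telephone. Section 6.1.1 names respiratory compromise due to the regimen among the study's adverse events. Section 7.1.6 identifies elderly or debilitated patients, and those with existing lung disease, as being at greater risk. Section 8.7 sets no formal stopping rule, so patient-level instructions carry more of the safety burden.

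**Working it through.** No arithmetic applies: the point depends on no rate, effect size, power or sample size. The check sets the instructions side by side and asks what each permits.

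| Source | Trigger | Patch | Tramadol |
|---|---|---|---|
| 7.1.5 | Respiratory depression observed, any grade | Must come off; oxygen and naloxone | Not addressed |
| Table 4, catch-all row | Respiratory depression listed, no grade | Clinician's choice | Clinician's choice |
| 5.2 | Intolerable side effects, with respiratory depression as an example | Off regimen | Off regimen |

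**Step 1: can the texts be followed together?** Yes. Table 4 permits removal, a reduction or no change; 7.1.5 permits only removal. Removal satisfies both. Section 5.2 then follows naturally: remove and rescue, then withdraw from the regimen. So 7.1.5 and 5.2 agree in direction, and Table 4 is the outlier.

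**Step 2: can Table 4 be followed without meeting 7.1.5?** Yes. Leaving the patch on, or only reducing its strength, fits Table 4 and breaches 7.1.5. This is the defect.

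**Step 3: does the adjective at the start of the Table 4 row separate the cases?** It can be read two ways.
- If it qualifies every item, severe respiratory depression is left to discretion.
- If it qualifies only nausea, all respiratory depression is left to discretion.

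Either way the row overlaps with 7.1.5, which names no grade.

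**Step 4: does any other text settle it?**
- Section 4.11 turns on whether an event is unacceptable, which is a judgement.
- Section 5.6 asks for monitoring and considered dose changes when a CYP3A4 inhibitor is given with the patch. That is preventive.
- Sections 7.1.4 and 7.2.4 warn against giving these drugs to patients with significant respiratory depression, but their examples are standing conditions such as severe COPD, asthma or myasthenia gravis. They are not rules for an acute event on treatment.
- The package-insert reference at the end of 7.1.8 covers other adverse events and does not rank 7.1.5 against Table 4.

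None of these states which instruction governs.

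**The case against.** The strongest reply is that nothing here is contradictory. Section 7.1.5 is a specific rescue instruction, Table 4 is a general dosing table, and a competent clinician will take the patch off. Much of that stands. A reader might infer that the protocol gives two orders that cannot both be obeyed, or three conflicting actions. The documents do not support either reading: discretion includes removal, and 5.2 and 7.1.5 fit in sequence. Section 5.2 can also be read as classing respiratory depression as intolerable by definition. That would make withdrawal mandatory, would cover tramadol too, and would narrow the tramadol gap.

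A reader might also infer from the QTc row that Table 4 was meant to copy the rules of 7.1.5 and dropped one. Section 7.1.5 says "buprenorphine should be held until it is less than 470 ms", and Table 4 has "Hold buprenorphine patch until QTc comes back to normal range <470 msec". The inference is weak. Table 4 adds a condition that other causes have been ruled out, which 7.1.5 lacks. It also omits the rules in 7.1.8 for stopping after severe skin reactions or anaphylaxis. It is not a complete list of actions, so a missing row proves little.

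Nor does the faulty pointer in 7.1.7 bear on this point. That text reads "No dose adjustments for liver or renal impairment required for TD buprenorphine. Refer to Table 3", whereas the table of that number is headed "Table 3: Adverse Events and Serious Adverse Events Reporting Requirements". The slip is clerical and concerns liver and renal dosing; correcting it would not settle how respiratory depression is handled.

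Two further mitigations are fair. Patients with a history of significant respiratory depression are excluded (section 4.10), and sections 1.3 and 7.1.2 describe a ceiling effect that limits it.

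What the reply does not remove is step 2. Table 4 expressly lists the event and permits a less safe action than 7.1.5 does. A division into acute rescue and later dosing is plausible, but neither section states it.

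**Conclusion.** The point holds as an internal safety inconsistency: one stated rule permits a less protective action than another stated rule for the same event. It should be fixed, but it is limited in scope. It is confined to one item in one table row, and a clinician who follows 7.1.5 breaks no rule.

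Its size cannot be put as a number of patients, because the documents give no rate for respiratory depression on this regimen. There is no effect on the sample size, the endpoint or the primary binomial test.

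The conclusion assumes that Table 4 may be consulted on its own during treatment. That is reasonable for a table devoted to dose modification of the two study drugs. It does not depend on which way 5.2 is parsed.

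**What to change.** Delete respiratory depression from the catch-all side-effects row of Table 4 and add a separate row:

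- **Buprenorphine:** remove the patch and manage per section 7.1.5.
- **Tramadol, or the oxycodone that has replaced it under Table 2:** hold during the acute event. The documents contain no such acute instruction, so this is a clinical addition for the investigator to confirm.
- **Afterwards:** off study regimen per section 5.2, with data monitoring continuing. Stating this without a further severity condition also settles how 5.2 applies to the event.

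As a separate clerical item, correct the table number in 7.1.7 from 3 to 4.

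The cost is a short protocol amendment: one new row, one item removed from an existing row, and one corrected number. Visits, sample size and analysis do not change.

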1. Patients found to be eligible for the study can be screened and enrolled anytime during first six weeks of radiation therapy. VAS pain scores will be recorded weekly using BPI questionnaires and daily using the pain app from the day of enrollment, as outlined in study calendar. Treatment with study regimen, collection of PROMIS[®], MDASI, CTCAE and other assessments like opioid drug use log, as outlined in the study calendar will start once the patient develops mucositis and has VAS \geq 4/10 pain score on the OM Pain App and BPI questionnaire (question 3: your pain at its worst in last 24 hours). Patients usually develop mucositis by the third or fourth week of radiation therapy so we anticipate treatment would begin by fourth week in most patients, but it may start sooner if the patient develops mucositis and has VAS \geq 4/10 pain. If a patient presents with radiation-induced mucositis pain on the day of enrollment, then, all study procedures, including PROMIS[®], MDASI-HN, and CTCAE will be completed that day. Visit procedures that were performed as standard of care prior to consent (without the specific intent to make the subject eligible for the trial), may count toward screening tests and eligibility if they are within the screening window of two days. Clinician follow-up will be scheduled weekly (1–7) and then on weeks 9 and 12.
2. If a subject is off the study drug regimen or the subject withdraws, then they will be followed as per follow-up requirements.
3. Serum chemistry values will include ALT/SGPT, AST/SGOT, alkaline phosphatase, bilirubin (total, direct, and indirect) creatinine, LDH, sodium, potassium, chloride, bicarbonate, calcium, phosphate, magnesium, BUN/urea, albumin, glucose. Serum chemistry results obtained from unscheduled visits should be entered into the electronic database. Additional serum

chemistry testing should be done as clinically indicated.

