4. Record of opioid pain medications, laxatives, and antiemetic use from the patient's drug diary will be copied by investigators on weekly clinic visits. This will commence after starting treatment. a) Patients will document pain and supportive medication use data daily in their diaries but that information will be verified and recorded by investigator/research coordinator during weekly clinic visits in the electronic medical record(EMR). This data is currently being collected in a section of pain app. Patients average weekly VAS pain scores (question 3 of BPI questionnaire) will also be documented in EMR during weekly clinic visits as per standard of care and can be used for study purposes.
5. The Oral Mucositis (OM) Pain App will be evaluated by the study team on a daily basis through a real-time pain assessment tool in the mobile app. Patients can start using the OM Pain App before starting therapy to familiarize themselves with the instrument. b) Pain app readings will be recorded up to four times/day. The daily pain data will be analyzed by the UWM research team on a weekly basis.
6. All questionnaires/forms can be recorded on weekly in-person visits from weeks 1–7 then completed weekly through in-person/telephone interviews by CTO staff from week 8–12. Other assessments can also be done over phone during week 8, 10 and 11. Window period of +/-3 days will be allowed for data collection.
7. EKG will be done at screening and then on week 7 and 12 if the patient is on treatment with Buprenorphine patch.
8. Digital photos will be taken to document mucositis on the day of enrollment, treatment initiation, then during week 9 and week 12 clinic visits.

=

LIST OF ABBREVIATIONS

AE	adverse event
ALP	alkaline phosphatase
ALT	alanine aminotransferase
ANC	absolute neutrophil count
AST	aspartate aminotransferase
AUC	area under the curve
BPI	Brief Pain Inventory
BUN	blood urea nitrogen
CBC	complete blood cell (count)
CDK	cyclin-dependent kinases
CQ	chloroquine
CR	complete response
CRC	clinical research coordinator
CRF	case report form
CSF	cerebral spinal fluid
CT	computerized tomography
CTCAE	Common Terminology Criteria for Adverse Events
CTL	cytotoxic T cell
CTO	Clinical Trials Office
DFS	disease-free survival
DLT	dose-limiting toxicity
DSMC	Data and Safety Monitoring Committee
DSMP	data and safety monitoring plan
ER	estrogen receptor
FDA	Food and Drug Administration
GCP	good clinical practice
GVHD	graft-versus-host disease

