4.9 Study Procedures: Follow-up Period (Week 8–12 from start of radiation therapy)

End-of-Treatment Procedures

To be completed by the CRC between week 8 to week 12. Refer to the study calendar for details.

- Record WHO mucositis grade.
- Brief Pain Inventory.
- ECOG/Zubrod Performance status.
- Evaluate and record potential other causes of mucositis (oral candidiasis, aphthous ulcer, infections, trauma, etc.).
- PROMIS® GI and cognition questionnaires recorded over phone or in person weekly.
- MD Anderson Symptom Inventory recorded over the phone or in person weekly.
- Oral cavity digital image collection to evaluate mucositis will be done on the day of treatment initiation, the end of week 9, and then week 12.
- Physical examination (demonstrating no pre-existing mucositis).

- Record adverse events, using CTCAE v.5.0.
- Record type of calorie intake (normal, liquid, soft, parental/enteral).
- Report IV fluids for hydration.
- Review OM Pain App device usage and proper reporting.
- OM pain data monitoring (VAS included in pain app). Data from week 9 will be used for primary endpoint analysis.
- Review bloodwork, including CBC and CMP.
- Review opioid log and record use of oral anesthetics, laxatives, and antiemetics at home. This data is currently being collected in a section of pain app. Patients average weekly VAS pain scores (question 3 of BPI questionnaire) because of radiation induced mucositis will also be documented in EMR during weekly clinic visits as per standard of care.
- Monitor opioid usage through WIPDMP.
- EKG will be performed at screening, week 7 and 12 for patients on buprenorphine patch

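### The buprenorphine hold for QTc above 500 ms has two triggers: Section 7.1.5 applies it to any such reading, Table 4 only once the cause is assigned to buprenorphine

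*Combined protocol and SAP*

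**What the plan says.** Section 7.1.5 names QT prolongation as a possible effect of buprenorphine and then gives an instruction with no condition on cause: "If QTc prolongation of more than 500 ms is noticed, then, buprenorphine should be held until it is less than 470 ms".

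Table 4, the dose-modification table in Section 7.2.8, has one row for QTc. Its entry condition is "Prolonged QTc>500 msec attributable to buprenorphine (other causes ruled out"). The action for the patch is "Hold buprenorphine patch until QTc comes back to normal range <470 msec", and the tramadol cell is marked as not applicable. The nearest other row covers "Other side effects, such as severe nausea, vomiting, headache, respiratory depression, somnolence, dizziness, and constipation" and leaves dose adjustment of both drugs to the clinician. It does not mention QTc.

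Footnote 7 of the Study Calendar sets the EKG schedule: "EKG will be done at screening and then on week 7 and 12 if the patient is on treatment with Buprenorphine patch". Section 6.1.1 lists a QTc above 500 ms among the established side effects of tramadol and buprenorphine together.

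**The concern.** A hold for a safety reading should have one trigger. The two statements agree on the drug, the threshold and the restart limit, but not on whether causality must be settled first. Staff who work from the dose-modification table, a natural place to look, find no instruction to hold while the cause is open. Staff who work from Section 7.1.5 hold at once.

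An open question of cause is foreseeable here. Exclusion criterion 15 in Section 4.10 admits patients on established antidepressants, antipsychotics and antiseizure drugs, and ends by promising periodic EKGs to watch the QTc. Section 5.6 warns that CYP3A4 inhibitors can raise buprenorphine concentrations. In such patients it may be hard to exclude every other cause, and that is where the two rules part. What is at stake is consistent handling of a safety signal. No statistical property of the trial is involved.

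**Working it through.** The defect is a matter of wording, so the main check sets the two rules side by side.

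| Situation, QTc above 500 ms | Section 7.1.5 | Table 4 |
|---|---|---|
| Assigned to buprenorphine, other causes excluded | Hold | Hold |
| Cause still being assessed | Hold | No instructed hold |
| Another cause possible and not excluded | Hold | No instructed hold |
| Assigned to another cause | Hold | No instructed hold |

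The rules agree in the first situation and differ in the other three. In all four the restart limit is 470 ms.

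Next, whether other text reconciles them. The remaining QTc statements are the entry limits (450 ms for men, 470 ms for women), the promise of periodic EKGs in exclusion criterion 15, and the adverse event list in Section 6.1.1. The EKG statements in the calendar and in Sections 4.8 and 4.9 give timing only. None states a hold rule or says which of the two governs.

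Last, the price of a hold. This sizes the cost of the instruction, not the defect.

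- Table 1 uses a 75:1 ratio. At 5 mcg/hr: 5 × 24 / 1000 × 75 = 9 mg morphine equivalent a day. At 20 mcg/hr: 20 × 24 / 1000 × 75 = 36 mg. Both match the table.
- Section 5.2 converts tramadol 50 to 400 mg as a range "which roughly translates to 5 mg to 40 mg MEDD", that is 0.1 mg per mg.
- Over the six titration steps in Table 2, with tramadol at the step maximum, the patch share is lowest at 5 mcg/hr with 250 mg: 9 / (9 + 25) = 26%. It is highest at 20 mcg/hr with 400 mg: 36 / (36 + 40) = 47%.
- At the 100:1 ratio that Section 5.2 also cites, the patch supplies 12 to 48 mg. The shares at the same two steps are 12 / (12 + 25) = 32% and 48 / (48 + 40) = 55%.

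**The case against.** The strongest reply is that both texts can be obeyed at once. Table 4 never says to leave the patch on, so a clinician who holds under Section 7.1.5 breaches nothing. Section 7.1.5 sits in the buprenorphine section, Table 4 in the tramadol section, and Section 4.11 lets the investigator stop treatment on judgment or for an adverse event with no test of cause. Section 7.1.5 is also headed as side effects, so drug causation may be implied. Exposure is narrow: patients with a long QTc are excluded at entry, EKGs on treatment fall at weeks 7 and 12, and the regimen runs only up to week 12.

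Much of this stands, and it limits the weight of the point. It does not remove the second trigger. The operative test in Section 7.1.5 is that the prolongation is noticed, and even with causation implied, Table 4 adds a step of excluding other causes that Section 7.1.5 lacks.

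A reader might infer more than the documents support:

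- *That Table 4 requires the patch to stay on, or that the trial has no hold for an unexplained QTc.* Table 4 is silent there, and Section 7.1.5 orders the hold.
- *That a work-up would be long.* Nothing says so. The scheduled chemistry (weeks 1 to 9 and 12) already includes "sodium, potassium, chloride, bicarbonate, calcium, phosphate, magnesium".
- *That the primary result is at risk.* Section 4.9 says "Data from week 9 will be used for primary endpoint analysis", a hold from the week 7 EKG would begin 9 − 7 = 2 weeks earlier, and one patient is 1/18 = 5.6 percentage points. Nothing in the documents shows that a hold turns a responder into a non-responder.
- *That raising tramadol to 400 mg a day is the natural cover.* Section 6.1.1 groups this event with tramadol as well. The not-applicable entry for tramadol makes sense only while the row is restricted to prolongation caused by buprenorphine.
- *That the existing oxycodone step covers a hold.* In Section 5.2 and Table 2 it follows 96 hours of pain above 3/10 on the highest dose of both drugs, with the patch continued.

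**Conclusion.** The inconsistency is real and rests on current text in both places. For a QTc above 500 ms whose cause is not yet established, Section 7.1.5 orders a hold and Table 4 gives none. It is worth correcting because it concerns a safety instruction and costs almost nothing to correct. It should not be presented as a missing safeguard or a statistical flaw.

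Its size cannot be calculated. The documents give no rate of QTc above 500 ms, and the number of patients affected may be zero among the 20 enrolled. Sample size, endpoint and analysis are unchanged. The conclusion assumes that the QTc row is read as the full instruction in Table 4. The row does not contain the word only, but it is the table's sole QTc entry and it is conditional.

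**What to change.** Delete the attribution condition from the Table 4 row, that is, everything after the 500 msec threshold. Both Section 7.1.5 and Table 4 should then read: hold the patch at any QTc above 500 ms while causes are assessed, and resume once it is below 470 ms.

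In the same row, change the tramadol cell from not applicable to clinician's discretion, since the cause may no longer be assumed to be buprenorphine. State that analgesia during a hold is also at the clinician's discretion. Do not name tramadol up to 400 mg a day, and do not write in oxycodone as if the existing step applied. Either would create a new rescue pathway.

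The cost is a wording amendment to one table row, with a matching phrase in Section 7.1.5. The clinical downside is an occasional temporary loss of the patch (9 to 36 mg morphine equivalent a day by Table 1) and a repeat EKG in a patient whose prolongation proves to have another cause. Section 7.1.5 already accepts that loss, so it is new only where Table 4 would have been followed.
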